7.2.6. COUNTING RULES FOR OCCURRENCES OF SOLICITED ADVERSE EVENTS

When the occurrences of solicited adverse events are summarized, each event recorded as having occurred during a specific period will be counted as only one occurrence regardless of the number of days on which it occurs.

For a given participant and the analysis of solicited symptoms within 7 days post-vaccination, missing or non-evaluable measurements will not be replaced. Therefore, the analysis of the solicited adverse events will include only vaccinated participants for doses with documented safety data (i.e., diary card completed). A diary card is considered complete when it has data recorded for all 7 days post vaccination. More specifically the following rules will be used:

- Participants who documented the absence of a solicited symptom after one dose will be considered not having that symptom after that dose.
- Participants who documented the presence of a solicited symptom and fully or partially recorded daily measurement over the solicited period will be included in the summaries at that dose and classified according to their maximum observed daily recording over the solicited period.
- Participants who documented the presence of a solicited symptom after one dose without having recorded any daily measurement will be assigned the value 'UNKNOWN'.
- Doses without diary cards documented will be excluded.

Document: \\dccar2dnetvnasc01p-lan1.quintiles.net\cp_ops\PROJECTS\Glaxo SmithKline\GSK205480_HAB61752\SAP
Author: PPD Version Number: 1.0
Version Date: 25OCT2022

Template No: CS_TP_BS016 – Revision 7
Effective Date: 01Nov2021

Reference: CS_WI_BS005

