5.2.2. SOLICITED SAFETY SET

All participants who received at least 1 dose of the study intervention (ES) who have solicited safety data for that intervention. The allocation in a group is based on the administered intervention.

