7.1.3. ADVERSE EVENTS

Solicited Adverse Events:

Daily recording of solicited adverse events: for diary cards indicating the presence or absence of solicited adverse events, for studies using paper diaries which have questions in the CRF indicating the presence or absence of solicited events the following rules are applicable:

- Denominators for the summary of administration site (or systemic) solicited adverse events will be calculated using the number of participants who respond "Yes" or "No" to the question concerning the occurrence of administration site (or systemic) adverse events.
- When a specific solicited adverse event is marked as having not occurred following a specific vaccination (i.e., SDTM FA.FAOCCUR=N for the specified post-vaccination period for the adverse event in question), all daily measurements will be imputed as Grade 0.
- When a specific solicited adverse event is marked as having occurred following a specific vaccination (i.e., SDTM FA.FAOCCUR=Y for the specified post-vaccination period for the adverse event in question), any missing daily recordings will be given imputed values to allow them to contribute to the 'Any' rows but not to specific grade rows of the solicited adverse event summary tables.
- When the occurrence of a specific solicited adverse event is not present (i.e. SDTM FA.FAOCCUR is neither Y nor N for the specified post-vaccination period for the symptom in question) but the group of solicited adverse events (administration site or systemic) is marked as having occurred (i.e. SDTM FA.FAOCCUR=Y), all missing daily recordings will be given imputed values to allow them to contribute to the 'Any' rows but not to specific grade rows of the solicited adverse event summary tables.

The following table shows how participants contribute to each category for a specific solicited adverse event over the Day X to Day Y post-vaccination period:

Document:	\dccar2dnetvnasc01p-lan1.quintiles.net\cp_ops\PROJECTS\Glaxo SmithKline\GSK205480_HAB61752\SAP		
Author:	PPD	Version Number:	1.0

Template No: CS_TP_BS016 – Revision 7
Effective Date: 01Nov2021

Reference: CS_WI_BS005

Solicited adverse event category	Participants included in the calculation of the numerator
Any	All participants with at least one occurrence of the adverse event at grade 1, grade 2, or grade 3 between Day X and Day Y or with the adverse event marked as present and at least one missing daily recording between Day X and Day Y

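### SAP 7.2.6 ties the solicited-event analysis to diary cards with all 7 days recorded, against its own bullets, 7.1.3 and the Solicited Safety Set; 7.1.3 and 7.2.6 also disagree on 'Any' in one narrow case

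*SAP*

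**What the plan says.** The lead-in to SAP 7.2.6 states that "missing or non-evaluable measurements will not be replaced". It therefore restricts the analysis to doses with documented safety data, glossed in brackets as a completed card, and then defines completeness: "A diary card is considered complete when it has data recorded for all 7 days post vaccination". The bullets are introduced by "More specifically the following rules will be used". The second bullet covers participants who documented a symptom: those with "fully or partially recorded daily measurement over the solicited period will be included in the summaries at that dose", classified by their maximum observed daily value. The third assigns UNKNOWN when a symptom was documented with no daily value. The fourth excludes only doses without a diary card.

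SAP 7.1.3 sets the denominator differently: "Denominators for the summary of administration site (or systemic) solicited adverse events will be calculated using the number of participants who respond". The response meant is a Yes or a No on whether an event of that group occurred. For a symptom marked present, "any missing daily recordings will be given imputed values to allow them to contribute"; what they contribute to is 'Any', never a particular grade. Its numerator table puts a participant in 'Any' with "at least one occurrence of the adverse event at grade 1, grade 2, or grade 3", or when the event is marked present and at least one day is missing.

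The Solicited Safety Set (SAP 5.2.2) takes exposed participants "who have solicited safety data for that intervention". Protocol Table 16 likewise sets no 7-day condition, and SAP 16.1 and protocol 9.4.1 make this the analysis set for solicited events.

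**The concern.** Solicited administration-site and systemic events are the first two primary endpoints. Protocol 9.4.1 reports them as participants with at least one, any, and Grade 3 events. The SAP gives two incompatible answers on who is analysed after a dose: everyone with a Yes/No answer, or only those with data on all 7 days. A programmer who filters on the 7-day definition would remove participants who recorded an event but missed a day, from numerator and denominator alike. The SAP also gives two answers on whether some incompletely recorded symptoms count in 'Any'. The study is descriptive and its groups have 6, 12 or 24 participants, so these percentages are the primary result and a single card can move one.

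**Working it through.** The plan states no figure on this point, so the check sets the rules side by side for one symptom after one dose.

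| Diary content | 7.2.6 lead-in, literal | 7.2.6 bullets | 7.1.3 |
|---|---|---|---|
| All 7 days recorded, some day Grade 1 or higher | 'Any' | 'Any' | 'Any' |
| A day missing, some recorded day Grade 1 or higher | dose dropped | 'Any', at maximum recorded grade | 'Any' |
| Marked present, a day missing, every recorded day Grade 0 | dose dropped | Grade 0 | 'Any' |
| Marked present, no daily value | dose dropped | UNKNOWN, row not stated | 'Any', no grade row |
| Marked absent, daily values missing | dose dropped | no symptom | Grade 0 |

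Row 2 shows the first conflict: the lead-in stands alone against the bullets and 7.1.3. Row 3 shows the second, which remains even if the bullets govern. It arises mainly for redness or swelling below 25 mm and temperature below 38.0°C, which SAP 16.1.3 grades 0. Row 4 is an open point.

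**Size per participant.** Group sizes are from protocol Table 4. The shift in a symptom row is 100/n:
- n=24: 100/24 = 4.2 points
- n=12: 100/12 = 8.3 points
- n=6: 100/6 = 16.7 points

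**Illustration.** The documents give no rate of missing diary days, so these inputs are assumptions: a group of 24, 10 participants with the symptom on complete cards, and k further participants with the symptom marked present and a day missing. All other cards are complete. Intervals are exact 95% Clopper-Pearson, the SAP 6.1 method.

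With k=3:
- Literal lead-in: 10/(24−3) = 10/21 = 47.6% (25.7 to 70.2).
- 7.1.3: (10+3)/24 = 13/24 = 54.2% (32.8 to 74.4). The bullets agree if the three each recorded a Grade 1 or higher day.
- 7.2.6 bullets, if the three recorded only Grade 0 days: 10/24 = 41.7% (22.1 to 63.4).

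With k=1 the three results are 10/23 = 43.5%, 11/24 = 45.8% and 10/24 = 41.7%.

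For a group of 12 with 5 events on complete cards:
- k=1: 5/11 = 45.5%, 6/12 = 50.0% and 5/12 = 41.7%.
- k=3: 5/9 = 55.6%, 8/12 = 66.7% and 5/12 = 41.7%.

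With k=0 the rules agree.

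**The case against.** The strongest reply is that the operative text points one way. The lead-in runs straight into specific rules that include partial recorders, and both the analysis set and the denominator lack a 7-day condition. One stray sentence is then all that needs removing. This is the likely reading, but the SAP does not state it, and under it the completeness definition has no function.

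On 'Any', the sections can be harmonised: 7.1.3 fills the 'Any' row and 7.2.6 assigns the grade. That is possible, but 7.2.6 rules out replacing missing values without limiting this to grade rows. The case is also narrow. For pain, headache, fatigue, myalgia and arthralgia, protocol Table 20 defines Grade 0 as none or normal, so a symptom marked present with only Grade 0 days would normally mean that it fell on the missing day.

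Three stronger inferences are not supported:
- **A Grade 3 result could vanish.** A reader might compute 1/24 (0.1 to 21.1%) becoming 0/23 (0 to 14.8%). That needs the literal lead-in, a single Grade 3 participant, and that same participant missing a day. If the bullets govern, Grade 3 does not change, because no section imputes a grade.
- **UNKNOWN contradicts 7.1.3.** It does not. UNKNOWN is compatible with counting the symptom in 'Any' and in no grade row; the SAP leaves the row unstated.
- **Dose-escalation decisions are affected.** SAP section 1 puts the safety committee analyses in separate documents, and the holding rules in protocol Table 11 count participants with events, not SAP table rows.

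Reminder calls at Day 4 and Day 172, and card return at Visits 2 and 5, should limit gaps. The output templates cited in SAP section 8 are not in the package and may settle the layout, but the conflicting SAP text would remain.

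**Conclusion.** The point holds in two parts. First, the completeness condition in 7.2.6 is wrong as written: it contradicts the bullets beneath it, the 7.1.3 denominator and the analysis set. The bullets probably override it, so the loss of partial diaries is a risk of literal programming and not the most likely planned analysis. Second, 7.1.3 and 7.2.6 give different 'Any' results for a symptom marked present with a missing day and only Grade 0 values. Each such participant moves the symptom row by one participant's share of the group. The administration-site or systemic group row moves only if that participant has no other event in that group.

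How often either case will occur is unknown, and with complete diaries neither arises. All analyses are descriptive (protocol 9.1), so no error rate, power or sample size is involved. The correction is still worth making because it concerns the counting rule for primary endpoints in small groups.

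**What to change.** In SAP 7.2.6:
- Delete the sentence that defines a complete card by 7 days of data, and the bracketed condition that the card be completed.
- State that the 7.1.3 Yes/No denominator governs, separately for each dose.
- Limit the statement that missing values are not replaced to the grade rows.
- State that the 7.1.3 'Any' rule applies in both sections, with UNKNOWN counted in 'Any' and in no grade row.

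Keep the existing 7.1.3 rule for a symptom left blank when its group is answered Yes; it is explicit and need not change. Check that the output templates match, and settle the wording before group-unblinded results are produced, so that the rule is not chosen with results in view.

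The cost is SAP wording and programming specification only, with no new data and no change to study conduct.

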7.2.7. GEOMETRIC MEAN CONCENTRATIONS (GMCs)/CCI

Geometric Mean Concentration (GMC),CCI calculations are performed by taking the inverse logarithm of the mean of the logCCI transformations.CCI
CCI. The cut-off value will be defined by the laboratory before the analysis.

8. OUTPUT PRESENTATIONS

The templates provided with this SAP describe the presentations for this study and therefore the format and content of the summary tables, figures and listings to be provided by IQVIA Biostatistics.

Some minor modifications may be necessary to the planned design of tables, figures, and listings to accommodate data collected during the actual study conduct.

9. DISPOSITION AND WITHDRAWALS

All participants who provide informed consent and were randomized or received study intervention or underwent a post-screening procedure will be accounted for in this study. Participant disposition will be tabulated for each step, each study treatment, and for all participants combined per step and overall (using the Enrolled Set) with the number of participants who did not meet eligibility criteria, randomly assigned to treatment, completed Day 29, complete Day 169, completed Day 197, complete Day 337, complete the study, prematurely discontinue, and the reason for early discontinuation. A listing will present dates of completion or early withdrawal and the reason for early discontinuation, if applicable, for each participant.

Listings of treatment discontinuation, participant visits, inclusion/exclusion criteria responses, study protocol deviations, treatment randomization and study treatment administration will be provided.

A listing of participants whose trial participation was impacted by COVID-19 will be presented along with the description of the impact.

Number of participants who discontinued study drug or study due to COVID-19 infection or issues related to the COVID-19 pandemic will be summarized for each study treatment, each step and for all participants combined.

10. DEMOGRAPHIC AND OTHER BASELINE CHARACTERISTICS

Individual participant demographics and baseline characteristics (medical history and results from viral serology, and urine pregnancy tests) will be presented in listings.

Demographic characteristics such as age, sex, race, height, weight, and body mass index (BMI) will be

Document: \\dccar2dnetvnasc01p-lan1.quintiles.net\cp_ops\PROJECTS\Glaxo SmithKline\GSK205480_HAB61752\SAP
Author: PPD Version Number: 1.0
Version Date: 25OCT2022

Template No: CS_TP_BS016 – Revision 7
Effective Date: 01Nov2021

Reference: CS_WI_BS005

summarized and tabulated for each treatment, each step and for all participants overall. Descriptive statistics (mean, median and standard deviation) will be presented for age, height, weight, and BMI. Frequency counts and percentages will be presented for sex, race, and step.

No statistical testing will be carried out for demographic or other baseline characteristics.

11. PROTOCOL DEVIATIONS

11.1. DEVIATIONS RELATED TO STUDY CONDUCT

A deviation from a protocol occurs when Investigator site staff or a study participant does not adhere to the Protocol's stipulated requirements, whether inadvertently or planned. Protocol deviations will be listed and will include a classification of minor or major, as determined by clinical staff.

Important protocol deviations will be reviewed by the study team to identify deviations which have the potential to affect the immunogenicity results.

11.2. DEVIATIONS RELATED TO IMMUNOGENICITY ANALYSIS

Changes to the procedures or events, which may impact the quality of the immunogenicity data, will be considered important protocol deviations and will be described within the clinical study report. These changes or events will include any circumstances that will alter the evaluation of the immunogenicity results. Examples include, but may not be limited to, sample processing errors that lead to inaccurate immunogenicity results, and/or inaccurate dosing.

Participants may be eliminated from the per-protocol set for analysis of immunogenicity if, during the study, they incur a condition that has the capability of altering their immune response or are confirmed to have an alteration of their initial immune status. Participants may also be eliminated from the per-protocol set as described in Section 7.2 and Section 9.3 of the protocol. Such scenarios will be discussed by the study team and decision to exclude a participant and/or data from the Per-protocol analysis set (Day 29, Day 169, Day 176 and Day 197) will be taken on a case-by-case basis.

Other deviations (not a comprehensive list) leading to elimination from the per-protocol set are:

- Invalid informed consent
- Fraudulent data
- randomization code broken
- dose volume insufficient
- vaccination not according to protocol
- vaccine dose storage conditions (temperature deviation)

Document: \\dccar2dnetvnasc01p-lan1.quintiles.net\cp_ops\PROJECTS\Glaxo SmithKline\GSK205480_HAB61752\SAP
Author: PPD Version Number: 1.0
Version Date: 25OCT2022

Template No: CS_TP_BS016 – Revision 7
Effective Date: 01Nov2021

Reference: CS_WI_BS005

- vaccine administered out of expiry date
- violation of inclusion/exclusion criteria

interval between doses

- two doses not in the same treatment group
- concomitant infection related to study vaccine or not related to study vaccine that may alter the immune response
- serology result at post vaccination not available for all assays (blood sample not available or result not available)

Protocol Deviation Management Plan (PDMP) describes the complete list of elimination codes that could lead to exclusion from the per-protocol set.

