7.2. Participant discontinuation/withdrawal from the study

A participant is considered to have withdrawn from the study if no new study procedure has been performed or no new information has been collected for him/her since the date of withdrawal/last contact.

From an analysis perspective, a study 'withdrawal' refers to any participant who did not return for the concluding Visit/Contact planned in the protocol.

Investigators will attempt to contact participants who do not return for scheduled visits or follow-up.

All data and samples collected up to and including the date of withdrawal of/last contact with the participant will be included in the study analyses.

The primary reason for study withdrawal will be documented in the eCRF, based on the list below:

- AEs requiring expedited reporting to GSK (refer to Section 10.3.10.1 for more details)
- Unsolicited non-serious adverse events
- Solicited adverse event
- Withdrawal by participant, not due to an adverse event*
- Migrated/Moved from the study area
- Lost to follow-up
- Sponsor study termination
- Other (specify)

*If a participant is withdrawn from the study because he/she has withdrawn consent and the reason for withdrawal was provided, the Investigator must document this reason in the eCRF.

Participants who are withdrawn from the study because of AEs/SAEs must be clearly distinguished from participants who are withdrawn for other reasons. Investigator will follow participants who are withdrawn from the study due to an AE/SAE until the event is resolved (see Section 10.3.8.2).

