9.3.1. Criteria for elimination from analysis

If the participant meets one of the criteria mentioned below or ones listed in the Section 7.1.1, he/she may be eliminated from per-protocol analysis.

- Use of any investigational or non-registered product (drug or vaccine) other than the study vaccine(s) used during the study period.
- Use of immunosuppressants or other immune-modifying drugs administered chronically (i.e., more than 14 days in total) during the study period. For corticosteroids, this will mean prednisone 20 mg/day (for adult participants), or equivalent. Inhaled and topical steroids are allowed.
- Use of any long-acting immune-modifying drugs (e.g., infliximab) administered at any time during the study period.
- Use of any immunoglobulins and/or any blood products administered during the study period.
- Use of any vaccine not foreseen by the Study Protocol administered during the entire period of participant's study participation.
- Use of foreseen vaccines outside the recommended time window.
- Unblinding after any study intervention has been administered.

Other criteria for elimination from analyses will be reported in the Statistical Analysis Plan (SAP) and in the Protocol Deviation Management Plan.

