10.10.2. Glossary of terms

Adverse event:	Any untoward medical occurrence in a patient or clinical investigation participant, temporally associated with the use of a medicinal product, whether or not considered related to the medicinal product. An AE can therefore be any unfavourable and unintended sign (including an abnormal laboratory finding), symptom, or disease (new or exacerbated) temporally associated with the use of a medicinal product. For marketed medicinal products, this also includes failure to produce expected benefits (i.e., lack of efficacy), abuse or misuse.
Blinding:	A procedure in which 1 or more parties to the trial are kept unaware of the intervention assignment in order to reduce the risk of biased study outcomes. The level of blinding is maintained throughout the conduct of the trial, and only when the data are cleaned to an acceptable level of quality will appropriate personnel be unblinded or when required in case of an SAE. In an observer-blind study, the participant, the site, and Sponsor personnel involved in the clinical evaluation of the participants are blinded while other study personnel may be aware of the treatment assignment. For this study, single-blind means the Sponsor will be aware of the study intervention assignment but the Investigator and/or his staff will not.
Caregiver:	A ‘caregiver’ is someone who 
• lives in the close surroundings of a participant and has a continuous caring role or• has substantial periods of contact with a participant and is engaged in his/her daily health care (e.g., a relative of the participant, a nurse who helps with daily activities in case of residence in a nursing home). In the context of a clinical study, a caregiver could include an individual appointed to oversee and support the participant’s compliance with protocol specified procedures.

Certified copy:	A copy (irrespective of the type of media used) of the original record that has been verified (i.e., by a dated signature or by generation through a validated process) to have the same information, including data that describe the context, content, and structure, as the original.
Combination product	Combination product comprises any combination of 
• drug• device• biological product Each drug, device and biological product included in a combination product is a constituent part.

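### SAP 11.2 cites the protocol's study-withdrawal section as a source of per-protocol exclusions, and does not require case-by-case exclusions to be decided blind

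*SAP*

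**What the plan says.** The Per-Protocol Set (PPS) is the first-line set for immunogenicity (protocol 9.3, SAP 15) and is defined by time point. SAP 11.2 says of removal from it: "Participants may also be eliminated from the per-protocol set as described in Section 7.2 and Section 9.3 of the protocol". The same paragraph covers conditions that alter the immune response. It continues: "Such scenarios will be discussed by the study team and decision to exclude a participant and/or data" from the Day 29, 169, 176 and 197 sets is made case by case. A separate, admittedly incomplete list of other deviations follows. The full elimination codes are left to the Protocol Deviation Management Plan (PDMP), which is not one of the two documents.

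The protocol's own rule is in 9.3.1: "If the participant meets one of the criteria mentioned below or ones listed in the Section 7.1.1, he/she may be eliminated from per-protocol analysis". Section 7.1.1 lists contraindications to a further dose. Section 7.2 concerns withdrawal from the study and says: "All data and samples collected up to and including the date of withdrawal of/last contact with the participant will be included in the study analyses". It also defines the term: "From an analysis perspective, a study 'withdrawal' refers to any participant who did not return for the concluding Visit/Contact planned in the protocol".

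On blinding, the protocol is observer-blind up to the first interim analysis (Step 2, Day 29) and single-blind afterwards (6.3.4, 9.5.1). Its glossary explains: "For this study, single-blind means the Sponsor will be aware of the study intervention assignment but the Investigator and/or his staff will not". SAP 4.3 has a separate unblinded IQVIA team run the first interim without individual listings. It treats the whole study team as unblinded at the second.

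A second-line analysis on the Full Analysis Set (FAS) is required when exclusions from the PPS reach 10% in any group at any time point (protocol 9.3, SAP 15).

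**The concern.** Two weaknesses meet in one paragraph of the SAP.

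- **The reference.** It points to a section that gives no ground for exclusion and leans towards keeping the data. Anyone applying it literally has to treat withdrawal itself as the ground.
- **The procedure.** The resulting decisions are discretionary, and neither document says they must be taken blind or fixed before unblinding. For much of the study the sponsor side of the study team may know the arm.

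At stake is the reading of the two full-dose groups. Protocol 9.2.2 says their results will guide later studies, protocol 9.1 mentions choice of formulation, and SAP 15 compares full dose with and without Alum directly. In groups of 24, a couple of discretionary removals are visible in the result.

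**Working it through.** **1. The references side by side**

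| Source | Grounds for PPS elimination |
|---|---|
| Protocol 9.3.1 | its own list, plus 7.1.1 |
| SAP 11.2 | protocol 7.2, plus protocol 9.3 |

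Section 9.3 contains 9.3.1, which brings in 7.1.1. The 7.1.1 criteria are therefore reached, but only indirectly. All that citing 7.2 adds is withdrawal. The protocol's amendment history records no renumbering of Section 7 that would explain the mismatch.

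**2. What withdrawal means here**

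The concluding contact is the Day 337 phone call (protocol 4.4). The last antibody sample is at Day 197 (protocol Table 9), 337 − 197 = 140 days earlier. Someone with both doses and all five samples who misses that call is a withdrawal for analysis.

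**3. Who decides, and when**

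The protocol glossary entry for the Safety Review Team places sponsor safety, clinical and statistics staff in the study team. For a Step 2 participant:

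- Day 29 data accrue under observer-blinding.
- Days 169, 176 and 197 follow the first interim, after which the protocol regards the sponsor as aware of assignment.
- A missed Day 337 contact comes later still, after the point at which the SAP has the whole study team unblinded.

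The exposure is therefore mainly in the Day 169, 176 and 197 sets, and in any later revision of the Day 29 set. The SAP (25 October 2022) is based on the August 2022 protocol and so predates the May 2023 amendment that introduced single-blinding.

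**4. The plan's own figures**

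24 × (1 − 0.12) = 21.12, rounded down to the protocol's 21 evaluable per full-dose group. The exact (Clopper-Pearson) 95% limits for x of n are the 2.5% quantile of Beta(x, n − x + 1) and the 97.5% quantile of Beta(x + 1, n − x). These reproduce all nine rows of protocol Table 15; for example, 12/21 = 57.1%, 34.0% to 78.2%.

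**5. What the FAS trigger lets through**

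| Group size | Largest number excluded below 10% | Next step |
|---|---|---|
| 24 | 2 (8.3%) | 3 (12.5%) triggers |
| 12 | 1 (8.3%) | 2 (16.7%) triggers |
| 6 | 0 | 1 (16.7%) triggers |

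**6. Size of the discretion in a full-dose group**

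Assume 16 responders among 24 with serology, and two exclusions.

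| Case | Result | Exact 95% CI |
|---|---|---|
| None excluded | 16/24 = 66.7% | 44.7% to 84.4% |
| Two responders excluded | 14/22 = 63.6% | 40.7% to 82.8% |
| Two non-responders excluded | 16/22 = 72.7% | 49.8% to 89.3% |

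The spread is 2/22 = 9.1 points. If both full-dose groups truly had 16/24, opposite choices in the two groups would create an apparent difference of the same 9.1 points.

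**The case against.** The strongest reply is that the reference is simply misdirected. Because 7.2 has no elimination criterion, eliminating participants as it describes points to nothing. A missed Day 337 call meets no exclusion in Table 16, 9.3.1, 9.3.1.1 or the SAP's list, and the Day 29 set looks only at deviations up to Day 29. This stands to the extent that neither document orders such a removal. It does not settle the matter, since the SAP names 7.2 as a source and hands the resulting cases to case-by-case decision.

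Four stronger readings are tempting, and the documents do not support them.

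- **That the SAP drops the 7.1.1 criteria.** It does not; they come in through 9.3.
- **That the SAP flatly contradicts 7.2.** Section 7.2 speaks of study analyses, not of the PPS, and the FAS could hold the data. But below the 10% trigger no FAS immunogenicity analysis is required, so the planned immunogenicity summaries would omit them.
- **That every exclusion is made by a team that knows the arms.** The case-by-case sentence covers immune-altering conditions and the 7.2 and 9.3 cases. Other deviations are listed, with the codes in the PDMP, which may contain review rules that cannot be seen here. Before the first interim the study is observer-blind, and protocol 9.5.1 says only that some assignments may be revealed by it. The laboratory is blinded to assignment, and under the protocol the investigator stays blinded throughout.
- **That the assumed 12% dropout could all be discarded selectively.** Three of 24 would turn 16/24 into 13/21 (61.9%) or 16/21 (76.2%), a 14.3-point spread. But 3/24 is 12.5%, so the FAS analysis would be triggered and would show the 16/24. The protocol also treats those three as not evaluable, not as participants with full serology.

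**Conclusion.** The concern holds in a limited form. SAP 11.2 cites a section that supplies no per-protocol criterion. Read literally, that makes a participant with complete serology a candidate for exclusion over a missed phone contact. It leaves these and related cases to a study team that may know the arm, with no stated requirement of blinded or prior decision.

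The FAS rule limits the effect but does not remove it. Up to 2 of 24 per full-dose group can be removed without triggering it, worth up to 9.1 points on the illustration. That figure assumes 16/24 responders, serology on all 24, both exclusions falling entirely on one outcome, and no other group reaching 10%. It is a ceiling for that scenario, not a forecast. One exclusion in a control group of 6 would by itself bring in the FAS analysis.

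No error rate is affected, because the analyses are descriptive and immunogenicity is secondary. The weight of the point comes from the use of full-dose results in development decisions.

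**What to change.** Make three changes to SAP 11.2:

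1. Replace the reference to protocol Sections 7.2 and 9.3 with Section 7.1.1 and Section 9.3 (including 9.3.1). Keeping 9.3 preserves the link to the PPS definition in Table 16.
2. State that withdrawal, or a missed Day 337 contact, is not by itself a reason for exclusion at time points already validly sampled.
3. Require case-by-case exclusions to be decided, dated and signed off by existing staff without access to allocation or serology results, before each interim or final unblinded run.

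No sample size or interval in the documents changes. The cost is a few lines of wording, one sign-off per analysis and a slightly earlier deadline for deviation review. If the PDMP already sets such a rule, a cross-reference to it would cover the third change.
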